20.3.4 Secondary Safety Endpoints

- Summary of C-SSRS.
- Summary of general safety profile, including AEs (serious and nonserious), vital signs and laboratory assessments by study period and over the entire study.

20.4 Subject Characteristics

20.4.1 Demographics

The demographic information will be summarized for each analysis population by treatment group.

20.4.2 Medical and Surgical History

Relevant prior medical conditions or procedures will be summarized by body system and treatment group.

20.4.3 Prior and Concomitant Medications

Prior and concomitant medications will be coded according to the WHO Drug Dictionary. The incidence (number and percent) of prior and concomitant medication use will be summarized by treatment group.

20.4.4 Subject Disposition and Exposure to Study Drug

Subject disposition will be summarized for all enrolled subjects. The number of subjects who complete the study and who do not complete the study along with the reasons for discontinuation from the study will be summarized.

20.5 Efficacy Analysis

20.5.1 Randomized Treatment Period

Summary statistics (n, mean, SD, median, minimum, and maximum) of the baseline value, the value at each scheduled post baseline evaluation, and the corresponding change from baseline for ALSFRS-R score will be presented by treatment group for all subjects in the mITT population and the Per-Protocol population.

ALSFRS-R change from baseline at postbaseline visits will be computed as:

Change = baseline value - postbaseline value

Baseline is defined as the value observed at randomization (Week 0).

The primary efficacy endpoint, change from baseline in the telephone administered ALSFRS-R total score at Week 36 in the Acthar treated group vs the placebo group, will be compared using a mixed model with repeated measures (MMRM) analysis method. ALSFRS-R total score change from baseline will be used as a dependent variable, and the model will include the fixed effects of treatment, visit (categorical covariate), treatment-by-visit interaction, and baseline ALSFRS-R score as continuous covariates. The null hypothesis is that the least squared mean contrast between Acthar and placebo groups at Week 36 equals zero. Significance tests will be based on least-squares means using a two-sided test at $\alpha = 0.05$ (two-sided 95% confidence intervals). An unstructured covariance matrix will be used to model the within-subject variance-covariance. If the unstructured covariance structure matrix results in a lack of convergence, the following tests will be used in sequence: heterogeneous Toeplitz covariance structure, heterogeneous autoregressive covariance structure, and compound symmetry covariance structure. The Kenward-Roger approximation will be used to estimate the denominator degrees of freedom. Least squares mean for each treatment group,

least squares mean difference, and 95% confidence intervals between the treatment groups and the corresponding p-value will be reported.

All “mean slope decline” type of secondary endpoints will be analyzed using random coefficient model. Change from baseline will be the dependent variable, and treatment time (in month, continuous) and treatment-by-time interaction will be fixed effects and intercept will be random effect. Baseline values will be adjusted. Estimates of slope for each treatment group, estimates of slope difference, 95% confidence interval and the corresponding p-value will be reported.

For all “change from baseline” type of secondary endpoints, the same approach as for the primary efficacy endpoint described above will be used.

The primary and secondary endpoints analyses will be performed for the mITT and Per-Protocol populations.

[REDACTED]

[REDACTED]

[REDACTED]

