Clinical research in ALS was relatively sparse until the 1990's. The increase in clinical trials has been spurred by many factors including insights into the potential pathophysiology, development of preclinical and in vitro models and the approval by FDA of a disease modifying treatment (Aggarwal and Cudkowicz, 2008; Berry and Cudkowicz, 2011; Leigh et al, 2004). The pathophysiology of ALS is complex and not well understood. Current theories include abnormal protein aggregation, abnormal RNA processing, abnormal mitochondrial functioning, glutamate excitotoxicity, apoptosis, oxidative stress, and neuroinflammation with microglial activation and T cell infiltration (Bedlack et al, 2007; Berry and Cudkowicz, 2011; Henkel et al, 2009; Lanka and Cudkowicz, 2008; Leigh et al, 2004; Mitchell and Borasio, 2007; Rothstein, 2009).

The discovery of the SOD1 mutations in fALS led to the development of transgenic rodent models that overexpress a specific SOD1 mutation. Subsequent rodent models involving other genetic mutations have also been developed (Lanka and Cudkowicz, 2008; Rothstein, 2009). In vitro models

have also explored the SOD1 mutations, as well as other potential pathophysiologic pathways (Lanka and Cudkowicz, 2008).

Riluzole, approved by FDA in 1995, was shown to have a modest impact on survival in patients with ALS, delaying time to death on average by 2 to 3 months with no change in functional outcomes (Miller et al, 2012; Mitchell and Borasio, 2007; US Department of Health and Human Services, 1995). Riluzole inhibits presynaptic release of glutamate and modulates sodium, potassium, and calcium channels which target neuronal excitation (Bedlack et al, 2007; Bellingham, 2011; Miller et al, 2012). Edaravone was approved by FDA in May 2017, and prior to that it was approved in Japan as a treatment for ALS (FDA, 2017). Edaravone is a free radical scavenger (Kikuchi et al, 2011), and has been shown in 1 controlled 24-week study to delay functional decline in patients with “early ALS” defined by fairly well preserved respiratory function (forced vital capacity [FVC] \geq 80%) and minimal functional decline (Tanaka et al, 2016).

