15.1 Methods of Assigning Subjects to Treatment Groups

15.1.1 Randomization and Stratification

Subjects will be randomized according to a computer-generated allocation scheme to receive either Acthar 0.2 mL (16 U) or placebo 0.2 mL. Both investigators and the subjects will be blinded to the treatment assignment. The randomization will be stratified for riluzole use (yes/no) and the predicted values of the 9-month decline rate of ALSFRS score from baseline (≤ 1 point change/month vs > 1 point change/month) generated from the prize winning algorithm of the DREAM Phil Bowen ALS Prediction Prize4Life Challenge ([Küffner et al, 2015](#)).

In the Randomized Treatment Period, for each stratum, a separate randomization scheme will be produced. A block randomization will be performed. Subjects will not be randomized in the Open Label Extension Period. The biostatistician will decide on the details at the time of the creation of the randomization scheme.

The DREAM Phil Bowen ALS Prize4Life Challenge was issued to promulgate development of algorithms that could predict disease progression in ALS. The algorithm developers were provided with a small subset of data from the PRO-ACT database that included 3 months of individual patient level clinical trial information that was to be used to predict disease progression over the subsequent 9 months. There were 37 algorithm submissions, and each algorithm was then evaluated on a separate data set from the PRO-ACT database. The 2 winning algorithms both predicted disease progression better than a baseline model and clinicians using the same data.

Mallinckrodt contacted the developers of 1 of the prize winning algorithms in order to apply the algorithm to stratify the subjects in a previous trial (QSC01-ALS-01, [Mallinckrodt, 2016a](#)). The algorithm was modified to only use the available variables as predictors, which were collected from subjects' Screening Visit. The algorithm was validated with a subset of PRO-ACT data, and the root mean square error of the validation is 0.517, which is very close to the original algorithm. In this study, the ALSFRS-R score collected at the Baseline Visit will be converted to ALSFRS score by dropping the last 2 questions (Questions 11 and 12) since most of the records in PRO-ACT database use ALSFRS scoring system.

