The algorithm will be implemented after the Screening Visit, and a 9-month decline rate in ALSFRS score will be generated based on the screening and baseline data, which will be used to stratify the subjects when they return for the Baseline Visit.

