20 STATISTICAL METHODS AND PLANNED ANALYSIS

20.1 General Considerations

This section provides a general description of the statistical methods to be used in analyzing both safety and efficacy data. The key statistical issues or considerations will be addressed. A more detailed statistical analysis plan will be provided in a separate document that will be finalized prior to interim analysis.

Unless otherwise specified, all statistical tests will be two-sided with a significance level of 0.05. Summary statistics will be provided for all study variables with descriptive statistics (number of observations, mean, standard deviation, median, minimum, and maximum) for numerical (or continuous) variables. Frequency and percentages will be calculated for categorical variables. Data summary and analyses will be performed with SAS 9.2 or higher.

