20.10 Statistical Power and Sample Size Considerations

The primary efficacy analysis will compare the mean telephone administered ALSFRS-R total score change from baseline at Week 36 in the group treated with Acthar to that in the placebo group using mITT analysis population. With 140 mITT subjects in the group treated with Acthar and 70 mITT subjects in the placebo group (210 subjects total), assuming the expected ALSFRS-R total score change from baseline of 6.3 and 9 in Acthar and placebo groups, respectively, the common SD of the ALSFRS-R total score change from baseline at Week 36 of 5.83 (estimated from PRO-ACT database), and dropout rate of 20% prior to Week 36, the study will have at least 80% power to detect the treatment difference at the 0.05 level of significance. Assuming a few subjects might not qualify for the mITT analysis population after randomization, approximately 213 subjects will be enrolled and randomized into Acthar treated group and placebo group in a 2:1 ratio.

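### The protocol's primary MMRM leaves out both randomisation strata; the test stays valid, but precision is given up if predicted decline is prognostic

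*Combined protocol and SAP*

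**What the plan says.** Section 15.1.1 sets the design: "The randomization will be stratified for riluzole use (yes/no) and the predicted values of the 9-month decline rate of ALSFRS score from baseline", with decline split at 1 point per month. It adds that "for each stratum, a separate randomization scheme will be produced. A block randomization will be performed". The predicted rate is therefore available for every subject at randomisation; it is the value "which will be used to stratify the subjects when they return for the Baseline Visit".

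Section 20.5.1, and the Synopsis in the same words, give the primary model term by term: "the model will include the fixed effects of treatment, visit (categorical covariate), treatment-by-visit interaction, and baseline ALSFRS-R score as continuous covariates". Neither stratification factor is listed. For the change-from-baseline secondary endpoints, "the same approach as for the primary efficacy endpoint described above will be used".

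No visible text gives a reason for the omission or plans a stratum-adjusted analysis. Section 20.11.2 covers sensitivity analyses for missing data only. Section 20.1 defers detail: "A more detailed statistical analysis plan will be provided in a separate document that will be finalized prior to interim analysis". That document was not supplied, and some text after the model description in Section 20.5.1 is redacted.

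**The concern.** Blocking within a prognostic stratum balances it across arms and so takes its contribution out of the true variance of the treatment contrast. A model that omits the stratum still counts that contribution as residual error. The standard error is then larger than the design warrants, the confidence interval too wide and the test conservative.

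There is reason to expect predicted decline to be prognostic. It forecasts nearly the same quantity as the primary endpoint: decline over 9 months, against change at Week 36 (36 × 7 / 30.44 = 8.3 months). Sections 9.1 and 15.1.1 say that the winning algorithms outperformed both a baseline model and clinicians. The planning assumption of a 9-point placebo change is 9 / 8.3 ≈ 1.1 points per month. That is close to the 1-point cut (ALSFRS-R against ALSFRS, so only roughly comparable), which suggests that both strata will be populated.

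At stake is the precision of the Week 36 estimate in a trial whose sample size was set for about 80% power.

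**Working it through.** **Inputs from Section 20.10.** Difference 9 − 6.3 = 2.7; SD 5.83; 140 and 70 mITT subjects; 20% dropout; two-sided 0.05. Completers: 140 × 0.8 = 112 and 70 × 0.8 = 56.

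**Reproducing the plan's figure.** SE₀ = 5.83 × √(1/112 + 1/56) = 0.954. Power is 80.3% by the noncentral t (80.8% by the normal approximation), which agrees with "the study will have at least 80% power to detect the treatment difference at the 0.05 level of significance". Solving for n gives 55 placebo and 165 in total; 165 / 0.8 = 207 after rounding up, against 210 planned. The strata are not needed to reach the stated power.

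**Assumption.** Let R² be the share of Week 36 change variance that the predicted-decline stratum explains beyond baseline score. The documents give no value. The validation root mean square error of 0.517 in Section 15.1.1 cannot be converted without the SD of the slopes. The range used is 0, 5, 10 and 20%, with riluzole set to 0%. With two equal strata, R² of 5, 10 or 20% means that the stratum means differ by 2 × 5.83 × √R² = 2.6, 3.7 or 5.2 points at Week 36.

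**Formula, single time point, 112:56 completers.** Under stratified randomisation the true SE is SE₀√(1 − R²), while the model without strata reports SE₀.

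- Power without strata = P(Z > (1.974·SE₀ − 2.7) / (SE₀√(1 − R²)))
- Power with strata = P(Z > 1.974 − 2.7 / (SE₀√(1 − R²)))
- Size without strata = 2·P(Z > 1.96 / √(1 − R²))
- Excess in reported SE = 1/√(1 − R²) − 1

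| R² | Power without | Power with | Gain (points) | Size without | SE too large by |
|---|---|---|---|---|---|
| 0% | 80.4% | 80.4% | 0 | 5.0% | 0% |
| 5% | 81.0% | 82.4% | 1.4 | 4.4% | 2.6% |
| 10% | 81.6% | 84.3% | 2.7 | 3.9% | 5.4% |
| 20% | 83.1% | 88.3% | 5.2 | 2.8% | 11.8% |

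A separate simulation of Week 36 change alone (213 subjects, blocked stratified 2:1 allocation, random 20% dropout, 8,000 trials per scenario) gave, without and with the strata:

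- R² = 0: power 80.5 and 80.6%; size 4.9 and 5.0%
- R² = 10%: power 81.6 and 84.4%; size 4.4 and 5.1%
- R² = 20%: power 82.6 and 88.3%; size 3.4 and 5.3%

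**Simulation of the planned MMRM.** Set-up: 210 subjects, 2:1 in blocks of 6 within four strata (assumed prevalence: predicted decline 50%, riluzole 60%); nine post-baseline visits; linear decline to 9 against 6.3; total SD 5.83 at Week 36; stratum effect growing linearly with time; remaining variance half random slope and half random walk, plus measurement error SD 1.2; 20% dropout spread evenly over visits; REML with unstructured covariance; 3,000 paired trials per scenario. The comparison model adds riluzole, predicted decline and predicted-decline-by-visit.

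| R² | Mean Week 36 SE, planned → added | Power, planned → added | Size, planned → added |
|---|---|---|---|
| 0% | 0.896 → 0.896 | 85.0 → 85.0% | 5.2 → 5.2% |
| 5% | 0.895 → 0.873 (−2.5%) | 85.1 → 86.7% | 3.9 → 4.6% |
| 10% | 0.894 → 0.850 (−4.9%) | 85.7 → 88.0% | 3.9 → 4.9% |
| 20% | 0.892 → 0.801 (−10.2%) | 87.7 → 92.3% | 2.9 → 5.5% |

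Monte Carlo error is about 0.4 points for size and 0.5 to 0.7 for power before pairing. Power exceeds 80% throughout because the MMRM recovers information from dropouts.

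**The interaction matters.** With both strata as main effects only, the Week 36 SE falls by just 0.4, 0.9 and 1.8% at R² of 5, 10 and 20%. A stratum effect that grows with time is poorly captured by a constant shift.

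**The case against.** The best counter-argument is that nothing in the plan fails. The test is valid and slightly conservative, the stated power is met, and choosing a simpler model is a legitimate preference. That is correct, and it limits this to a point about efficiency.

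Second, every non-zero gain rests on an assumed R². The stratum is a two-level split, and the largest figures need stratum means about 5.2 points apart beyond what baseline score explains, against an assumed mean placebo change of 9. This also stands: the gain could be nil, and the middle of the range is a more natural expectation than the top.

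Third, most of the gain comes from the by-visit term and not from merely listing the factors. That is true, and it is why the recommendation includes the term.

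Fourth, riluzole may contribute nothing. Section 9.1 describes the drug's effect ("delaying time to death on average by 2 to 3 months with no change in functional outcomes"), which does not show whether users and non-users differ in prognosis. The 0% used here is an assumption, and no part of the gain relies on riluzole.

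Fifth, the simulation's covariance and dropout patterns are assumed, and it used completers minus 3 degrees of freedom in place of Kenward-Roger. The closed-form results and the simpler simulation nevertheless agree in direction and approximate size.

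Finally, the unseen SAP or the redacted text may already include the strata. That cannot be excluded. It does not change what the protocol's visible model says.

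**Conclusion.** The concern holds for the protocol text. The primary MMRM omits both factors used to stratify randomisation, without explanation, and the change-from-baseline secondary models inherit the omission. Type I error is not inflated and the sample size is not wrong. If predicted decline explains 5 to 20% of Week 36 variance beyond baseline score, the planned analysis forgoes a reduction in standard error of about 2.5 to 10% and roughly 1.5 to 5 points of power. If it explains none, nothing is lost.

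These figures depend on the assumed R², stratum prevalence, a stratum effect growing linearly with time, and dropout unrelated to the strata. If dropout depends on predicted decline in a way the observed scores do not capture, the omission could also affect bias; the calculations do not test that. The change is worth making, but the trial's validity does not depend on it.

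**What to change.** In the primary MMRM, and in the change-from-baseline secondary models that follow it, add the riluzole stratum and the predicted-decline stratum as fixed effects, plus a predicted-decline-by-visit interaction. Using the continuous predicted rate, or adding baseline-by-visit, is optional. The slope models in Section 20.5.1 also name neither factor, so the same decision should be recorded for them. If the sponsor prefers the current model, give the reason. Either way, settle it before the SAP is finalised ahead of the interim analysis.

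The cost is wording only, since the stratification variables are already held for every randomised subject. The primary model gains ten fixed-effect parameters (1 riluzole + 1 predicted decline + 8 interaction terms over nine visits) with about 210 subjects. With R² = 0 the added terms left the simulated standard error at 0.896 and power at 85.0%, so there is no visible penalty if the strata prove uninformative.

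### The primary MMRM gives baseline ALSFRS-R one coefficient for all nine visits, so the Week 36 contrast may receive only part of the baseline adjustment, or a mis-signed one

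*Combined protocol and SAP*

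**What the plan says.** Section 20.5.1, repeated in the Synopsis, takes change from baseline in the telephone ALSFRS-R as the dependent variable, with fixed effects of treatment, visit as a categorical term, "treatment-by-visit interaction, and baseline ALSFRS-R score as continuous covariates". Change is defined as baseline minus postbaseline, so a positive value is decline. The null hypothesis concerns the least-squares contrast at Week 36. The covariance is unstructured, with heterogeneous Toeplitz, heterogeneous autoregressive and compound symmetry as successive fallbacks. The same section carries this approach to the secondary endpoints of the change-from-baseline type.

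The schedule of events and Sections 14.3 to 14.5 give nine postbaseline telephone assessments, every four weeks from Week 4 to Week 36.

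Section 20.10 states that "the study will have at least 80% power to detect the treatment difference at the 0.05 level of significance". It uses the SD of the change itself and mentions no reduction for baseline adjustment. Sections 20.1 and 20.5.2 leave further detail to a separate statistical analysis plan, which is not among the documents.

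**The concern.** Treatment may act differently at each visit, but the baseline effect may not. If subjects with higher baseline scores decline faster or slower, that relation should be weak at Week 4 and stronger at Week 36. A single coefficient must compromise. With an unstructured covariance the compromise is a generalised-least-squares average dominated by visits where change has little variance, which are the early ones. The Week 36 contrast is then corrected for a chance baseline difference with a coefficient that largely describes the first months.

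At stake is precision at the one visit that decides the trial, in a design whose completer-based power is only just above 80%. The same model form is reused for secondary endpoints.

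**Working it through.** **Inputs from the documents.** Difference 9 − 6.3 = 2.7; SD of Week 36 change 5.83; 140 and 70 mITT subjects; "dropout rate of 20% prior to Week 36"; two-sided 0.05; nine visits.

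**Inputs assumed, because the documents give none.** Correlation r of baseline with Week 36 change ±0.2 or ±0.3; baseline SD σ_B = 5.5; rating-error SD σ_e from 0.5 to 2; true-change covariance random-slope, Brownian, or a 70:30 mixture.

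**Step 1: reproduce the stated power.** Completers are 0.8 × 140 = 112 and 0.8 × 70 = 56. The standard error is 5.83 × √(1/112 + 1/56) = 0.954 and the noncentrality 2.7/0.954 = 2.83. With 166 degrees of freedom power is 80.3% (80.8% by the normal approximation). The statement of at least 80% reproduces with no baseline adjustment.

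**Step 2: visit-specific coefficients.** The Week 36 residual SD is 5.83 × √(1 − r²): 5.712 for |r| = 0.2 and 5.561 for |r| = 0.3. Power is 81.9% and 83.9%.

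**Step 3: the single coefficient.** Let b hold the true visit-specific baseline coefficients and R the residual covariance. With treatment-by-visit saturated and complete data, the common coefficient is β = (1′R⁻¹b)/(1′R⁻¹1). Write s = β/b₃₆ for the share of the Week 36 coefficient that it keeps. The variance reduction at Week 36 is r²(2s − s²), against r² with the interaction.

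Two forms of b were used, with t = week/36:
- proportional to time: cov(baseline, change) = r·σ_B·5.83·t;
- with rating error: σ_e² + (r·σ_B·5.83 − σ_e²)·t. Error in the baseline score is part of baseline minus postbaseline at every visit.

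Example, rating-error form, r = 0.3, σ_e = 1.5, random slope. b₃₆ = 0.3 × 5.83/5.5 = 0.318. The Week 4 coefficient is [2.25 + (9.62 − 2.25)/9]/30.25 = 0.101. β comes out at 0.092, so s = 0.29. The variance cut is 0.09 × (0.58 − 0.084) = 4.5%, the SD 5.70 and power 82.1%.

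| r | form of b | covariance, σ_e | share s | variance cut | power, single | power, by visit | gain (points) |
|---|---|---|---|---|---|---|---|
| 0.2 | proportional | slope, 1.5 | 5% | 0.4% | 80.5% | 81.9% | 1.4 |
| 0.3 | proportional | slope, 1.5 | 6% | 1.0% | 80.7% | 83.9% | 3.2 |
| 0.2 | rating error | slope, 1.5 | 39% | 2.5% | 81.3% | 81.9% | 0.6 |
| 0.3 | rating error | slope, 1.5 | 29% | 4.5% | 82.1% | 83.9% | 1.8 |
| 0.2 | rating error | Brownian, 2 | 70% | 3.6% | 81.8% | 81.9% | 0.1 |
| −0.3 | rating error | slope, 2 | −35% | −7.4% | 77.5% | 83.9% | 6.4 |

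Over the whole grid, both forms together:
- positive r: s from about 1% to 70%; single-coefficient power 80.3% to 83.1%; gain from the interaction 0.1 to 3.5 points;
- negative r: s from about −53% to 22%; power 77.5% to 81.7%; gain about 1 to 6 points.

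Under the compound-symmetry fallback all visits weigh equally, so in the proportional form s is the mean of 1/9, 2/9, …, 9/9, which is 56%.

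**Step 4: check with dropout.** The model was fitted to 300 simulated trials per scenario, 140:70 with 20% monotone dropout. The share kept was 0.14, 0.30, −0.08 and 0.18 in four scenarios. In the first (random slope, σ_e = 1, r = 0.3) the empirical SD of the Week 36 contrast was 0.842 with no baseline term, 0.834 with one coefficient and 0.806 by visit. In the third (r = −0.3) the values were 0.852, 0.858 and 0.818. Treatment estimates hardly differed between models within a scenario (−2.58 to −2.71 across all; true −2.7).

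**The case against.** A main-effect baseline covariate is a legitimate prespecified choice in a randomised comparison. Nothing here threatens type I error, and the unseen analysis plan may already contain the interaction. The validity point stands. The second does not remove the issue, because Section 20.5.1 already enumerates the model terms; it does mean that confirmation there would suffice.

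A reader might infer that almost none of the adjustment reaches Week 36. That follows only if the baseline effect is proportional to time and rating error is small. With rating error carried into the change score, the Week 4 relation is not near zero, and at positive r the single coefficient can keep more than half of the Week 36 value.

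A reader might also infer that the power statement fails. It takes no credit for baseline adjustment, and the 80.3% gives no credit for the partial data of dropouts that a mixed model uses. Single-coefficient power falls below 80% only with negative r and appreciable rating error.

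Finally, one might infer bias when dropout depends on baseline. The omitted term is common to both arms, so harm to the contrast would generally need baseline-related dropout that differs by arm. The simulated dropout was unrelated to baseline, so it does not test this. The documents give nothing from which to quantify it.

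**Conclusion.** The point holds as a matter of efficiency. As written, the Week 36 contrast receives a baseline adjustment set mainly by the early visits. It may be partial or, if higher baseline goes with less decline, of the wrong sign. In power terms the loss against the interaction model is about 0.1 to 3.5 points for positive r and about 1 to 6 for negative r. Correction of a chance baseline imbalance is weaker to match.

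The direction of the weighting follows from the model. The size does not: it depends on the assumed r, rating error, baseline SD and covariance shape. No bias or inflation of type I error has been shown, and the sample-size statement stands on its own inputs. This is a worthwhile improvement, not a defect that invalidates the analysis.

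**What to change.** Add the baseline ALSFRS-R-by-visit interaction to the fixed effects of the primary model in Section 20.5.1 and the Synopsis. Add the matching baseline-by-visit term to the change-from-baseline secondary analyses that reuse the approach. If the sponsor prefers the single coefficient, the analysis plan should say why, before unblinding.

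The cost is 8 further fixed-effect degrees of freedom (nine coefficients in place of one) with about 210 subjects. No new data are needed, and neither the endpoint nor trial conduct changes. If the baseline effect is in fact constant over time, the term gains little.
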